3.1 STUDY SUCCESS AND TEST OF THE STUDY'S PRIMARY HYPOTHESIS

This study is designed to show that the investigational device (Cementless) is non-inferior to the Control device using four co-primary study endpoints. This will be shown using a closed testing method in which each of the primary endpoints specified above are compared using α =0.05. Study success requires that the Cementless group successfully demonstrate non-inferiority when compared to the Control group for all four of the individual primary endpoints, using the statistical methods described below. Because non-inferiority must be successfully shown for all four endpoints for study success, the type I error rate is preserved at 5% for the entire primary endpoint.^b The individual non-inferiority hypotheses for each of these four tests are as follows:

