3.1.1. RADIOGRAPHIC SUCCESS

The proportion of radiographically successful knees in the Cementless group is non-inferior to the proportion of radiographically successful knees in the Control group using an 8% margin of non-inferiority. The test is based on the upper bound of a one-sided 95% confidence interval for the difference, Control minus Cementless, of proportions of success at 22+ months. A conclusion of non-inferiority is supported if the upper bound of the confidence interval is 0.08 or less. In addition, a Fisher's Exact p-value will also be computed to test this hypothesis.

In this analysis, each knee will be considered as a separate case, and unilateral and bilateral subjects will be analyzed together, providing the unilateral and bilateral groups are poolable per sensitivity analyses given in Section 3.1.5°.

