3.1.5. SENSITIVITY ANALYSES - UNILATERAL AND BILATERAL KNEES

To address the impact of possible correlation occurring due to including two knees from the same patient, for the two endpoints that will incorporate bilateral knees (Radiographic Success and Absence of Revision/Removal/UADE), additional sensitivity analysis will be conducted in order to address any potential correlation occurring due to including two knees from the same patient. These are to include:

- a. An analysis that considers only unilateral subjects.
- b. A repeated measures model approach that can account for possible correlation within subjects.
- c. An analysis of data at the patient level, in which a patient is considered a "failure" if either knee fails.

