Type I error: conclude that the difference p_C - p_I is less than δ when in fact the difference is greater than or equal to δ , *i.e.* conclude that the experimental treatment is non-inferior to the control treatment when the control treatment is actually substantially better.

Statistics in Medicine 9(1990) pp 1447-1454.

^eFarrington and Manning

[&]quot;Test statistics and sample size formulae for comparative binomial trials with null hypotheses of non-zero risk difference for non-unity relative risk".

Type II error: conclude that the difference is greater than or equal to δ when it is actually less than δ , *i.e.*, conclude that the experimental treatment is inferior to the control treatment when the experimental treatment is essentially just as good.

Assumptions:

$\alpha = 0.05$	Probability of Type I error
$\beta = 0.90$	Probability of Type II error: power = $1 - \beta$
$p_{C} = p_I = 0.95$	Estimated success rate for control and treatment groups
δ = 0.08	Non-inferiority Margin

Resulting sample sizes (number of knees), not adjusted for attrition, are 191 Cementless device vs. 96 Control (5% type I error rate, 90% power). We increase our sample size by 10% to allow for possible exclusions in the primary analysis due to bilateral patients who may not be poolable with the unilateral cases, as well as attrition of up to 15%. This gives a sample size of 383 total subjects (255 Cementless vs. 128 Control).

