3.5.2. ANALYSES OF STUDY POPULATION

Analysis for primary and secondary endpoints will use the Per Protocol population, which consists of those cases with complete data for one or more of the primary endpoints collected per the protocol at the 22+ month follow-up visit (or, as described below in the section on Missing Data, at the last or next available visit if the primary endpoint in question is missing at the 24- month visit). The exception to this is the primary endpoint of Absence of Revision/Removal/UADE, which is cumulative; therefore all cases that have failed at or prior to 24 months due to a revision or UADE will be included in the analysis of that primary endpoint. For each primary endpoint, all available data will be used, even if the subject has missing data for one or more of the other endpoints. Since indications and inclusion/exclusion criteria are exactly the same for both device groups, and because randomization is received at the time of surgery, it is expected that few patients will fail to receive the assigned treatment. However, in the event that they do not, the primary analysis will use the device that was actually implanted if it was a study device; if a study device is not received, the patient will not be included in the primary analysis.

Bilateral patients will be used in the primary analysis for the of Radiographic Success and Absence of Revision/Removal/UADE endpoints, but will be analyzed separately for the Knee Society Function and Assessment endpoints. The bilateral patients will not be included in the primary analysis for the Knee Score endpoints, as there is no way to ensure that the knee scores for one knee will not be affected by the other. The sample size has been increased by 10% to allow for this, a percentage based on the bilateral enrollment in the post-approval study for the OxfordTM Menisal Unicompartmental Knee System.

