3.5.6. EXPLORATORY ANALYSES OF THE PRIMARY OUTCOME INCLUSING CENTER EFFECTS

The association between each primary endpoint and device group at 22+ months across sites will be examined using either an analysis of variance (continuous endpoint) or the Breslow-Day test for homogeneity of odds ratios (binomial endpoint). Sites with less than or equal to 5 cases in either treatment will be combined to form a "pooled" site for analysis. A significant p-value indicates heterogeneity of odds ratios of clinical success across sites, and in this case the proportions of success for each site will be examined graphically and descriptively to assess site dependency.

In addition, the association between device group and each primary endpoint for unilateral and bilateral subjects will be examined using either an analysis of variance or the Breslow-Day test for homogeneity of odds ratios. The test for center effects will use a p-value of 0.05. If there is no evidence of treatment*center interaction ($p \ge 0.05$), data will be pooled across centers. However, the existence of a quantitative interaction between treatment and center does not necessarily invalidate the analysis in pooling data across centers. Thus, if p < 0.05 then the observed proportions for each site will be examined graphically to assess site dependency as well as whether or not a qualitative interaction exists. Further, the sites contributing to this interaction will be examined, and if necessary, a stratified analysis will be conducted and results compared to overall study results to assess consistency.

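### Whether bilateral knees stay in the deciding analysis of the two binary co-primaries is left to an undefined, outcome-based poolability judgement, and Sections 3.3 and 3.5.2 disagree about the consequence

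*Combined protocol and SAP*

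**What the plan says.** Four parts of the SAP bear on which knees decide the two binary co-primaries.

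- **Sections 3.1.1 and 3.1.2** treat each knee as a case and analyse unilateral and bilateral subjects together, "providing the unilateral and bilateral groups are poolable per sensitivity analyses given in Section 3.1.5".
- **Section 3.1.5** lists three analyses: (a) "An analysis that considers only unilateral subjects", (b) a repeated-measures model, and (c) a patient-level analysis in which failure of either knee is failure of the patient. Its stated aim is to address correlation between two knees of one patient. It gives no test, threshold, timing or decision-maker for poolability, and no fallback if pooling is rejected.
- **Section 3.3** includes a 10% sample-size allowance for "possible exclusions in the primary analysis due to bilateral patients who may not be poolable with the unilateral cases".
- **Section 3.5.2** says, without condition, "Bilateral patients will be used in the primary analysis for the of Radiographic Success and Absence of Revision/Removal/UADE endpoints". It leaves bilateral patients out of the primary knee-score analyses and gives that as the reason for the 10% increase.

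Section 3.5.6 compares device effects between unilateral and bilateral subjects (ANOVA or Breslow-Day) as an exploratory analysis. The only p-value threshold there, 0.05, is for center effects. For centers it adds that "the existence of a quantitative interaction between treatment and center does not necessarily invalidate the analysis in pooling data across centers", and it responds to heterogeneity by inspection and, if needed, stratification.

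**The concern.** The conditional wording in 3.3 fits only the two binary endpoints, because bilateral patients are always outside the primary knee-score analyses. So 3.3, read with 3.1.1 and 3.1.2, gives one deciding set (unilateral knees, if pooling is rejected), and 3.5.2 gives another (all knees, always).

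The choice between them would be made from outcome data, since all three analyses in 3.1.5 are analyses of the endpoint itself and one of them is the unilateral-only result. The bilateral knees most likely to be judged not poolable are those in which the device effect differs. If the cementless device did worse there, those failures would leave a radiographic and a safety co-primary. Inclusion criterion 2 admits bilateral arthroplasty, so these patients belong to the population under study.

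Section 3.1 rests its 5% error claim on all four endpoints having to pass. That argument needs each component test to hold its own level, which an analysis set chosen after seeing outcomes does not guarantee.

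**Working it through.** **1. The plan's own figure.** Inputs from 3.3: success 0.95 in both arms, margin 0.08, one-sided alpha 0.05, power 90%, ratio 2:1. With the simple normal approximation:

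n(control) = 0.95 × 0.05 × 1.5 × (1.645 + 1.282)² / 0.08² = 95.3, so 96; n(cementless) = 2 × 95.34 = 190.7, so 191.

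Dividing by 1 − 0.10 − 0.15 = 0.75 gives 254.7 and 128.0, so 255 + 128 = 383. The plan's numbers reproduce; the sample size is not in question.

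**2. Can the two readings give different decisions?** The rule is that "A conclusion of non-inferiority is supported if the upper bound of the confidence interval is 0.08 or less". The bound in 3.2 is (pC − pI) + 1.645 × √[pC(1 − pC)/nC + pI(1 − pI)/nI]. Taking 15% attrition from 255 and 128 leaves 217 and 109 knees. For illustration, let 10% of these be bilateral (22 and 11).

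| Knees | Failures, cementless | Failures, control | Difference | SE | Upper bound | Against 0.08 |
|---|---|---|---|---|---|---|
| Unilateral | 10/195 | 5/98 | 0.0003 | 0.0273 | 0.045 | pass |
| Bilateral | 8/22 | 0/11 | | | | |
| All | 18/217 | 5/109 | 0.0371 | 0.0274 | 0.082 | fail |

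The Breslow-Day p-value is 0.038, so a conventional 0.05 test would call these groups heterogeneous. For the 0.10 margin of 3.1.2, the same unilateral counts with 12/22 vs 0/11 bilateral failures give an all-knee bound of 0.103 (fail) against 0.045 (pass).

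Not every disagreement would trip such a test. Unilateral failures of 12/178 vs 4/89 with bilateral failures of 9/39 vs 1/20 give bounds of 0.070 (unilateral, pass) and 0.098 (all knees, fail), but Breslow-Day p is 0.28. There the decision changes only if mere disagreement with analysis (a) counts as not poolable.

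**3. Effect on the error rate.** Assumptions, none of them in the plan: a Breslow-Day gate at p < 0.05, control failure 5%, independent knees, and 10% of patients bilateral. That makes 20/110 = 18% of knees bilateral: 178/89 unilateral and 39/20 bilateral. The true all-knee deficit is set at about 8 points, so any pass is a false one. Simulated pass rates for the radiographic endpoint:

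| Deficit, unilateral / bilateral (points) | All knees decide | Gate, then unilateral only |
|---|---|---|
| 8 / 8 (no heterogeneity) | 4.4% | 4.4% |
| 6 / 17 | 4% | 7% |
| 5 / 22 | 4% | 11% |
| 9 / 4 (opposite direction) | 4.1% | 3.8% |

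With 10% of knees bilateral, a 6-point unilateral deficit needs about 26 points in bilateral knees to reach the same all-knee deficit, and the rates are 4.2% and 6.6%. Larger inflations need larger gaps still.

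**4. Power if all knees always decide.** With 217 and 109 independent knees and 95% success in both arms, power is 93.1%. With a design effect of 1 + (bilateral share × ICC), it is 90.9-92.5% at a 10% share (ICC 1.0 down to 0.3) and 88.7-91.8% at a 20% share. Unilateral-only analysis of 195 and 98 knees has 90.7%.

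**The case against.** A reader might infer that the SAP lets a unilateral-only pass stand in for a failed all-knee result. The documents do not say so. Sections 3.1.1 and 3.1.2 name no fallback. Exclusion appears only in one tentative clause of the sample-size section, while the section that governs analysis sets, 3.5.2, keeps bilateral patients in. Section 3.5.4 likewise pools radiographic and safety outcomes for the secondary analyses. The clause in 3.3 may be loose wording for the knee-score exclusion. Section 3.1.5 is about correlation, and its analyses (b) and (c), which exclude nobody, are equally natural fallbacks. All of this stands, and it is why the point is an unresolved conflict rather than a declared rule.

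The size is also open to challenge. The gate is assumed, the 17-22 point bilateral deficits are large and nothing in the documents predicts them, the effect vanishes without heterogeneity, and it reverses slightly if bilateral knees do better. These are per-endpoint rates, and study success still needs all four endpoints. Bilateral failures would remain visible in the adverse event comparison (3.5.3), the Kaplan-Meier curves (3.5.4) and the ITT sensitivity analysis (3.4.2). These limits hold too.

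Footnotes to 3.1.1 and 3.1.2 cite agreement at an FDA pre-submission meeting. The content of that agreement is not in the documents, so it neither supplies a criterion here nor removes the conflict with 3.5.2.

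**Conclusion.** The concern holds as a conflict with a consequence. Sections 3.1.1, 3.1.2 and 3.3 make the presence of bilateral knees in two deciding analyses depend on an undefined judgement from outcome data; 3.5.2 does not. On the first reading the exclusion can reverse a decision (0.082 against 0.045). Under the assumed gate and share it raises per-endpoint false non-inferiority from about 4% to 7-11%, but only if the cementless device does much worse in bilateral knees.

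It would go too far to say that the plan's error rate is inflated in general, since the figure stays near 4.4% without heterogeneity. It would also go too far to say that the plan supports a claim for bilateral use after leaving bilateral failures out; no labelling text in the documents supports that. The point merits correction before the data are examined, because the repair is cheap and removes the ambiguity whichever reading was meant.

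**What to change.** Reconcile the sections in favour of 3.5.2:

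- Delete the poolability condition in 3.1.1 and 3.1.2.
- In 3.3, limit the 10% allowance to the knee-score endpoints.
- State that the all-knee analysis always decides both binary co-primaries, and replace the independent-samples interval in 3.2 for these endpoints with one that allows for within-patient correlation. The note to Section 2.2 says that a later contralateral study knee receives a matching device and is not randomized, so correlation belongs in the interval and is not a reason for exclusion.
- Keep the unilateral-only and patient-level analyses of 3.1.5 as sensitivity analyses, and report the unilateral and bilateral differences separately with intervals.
- State that a unilateral-only pass cannot replace a failed all-knee result.

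The cost is SAP wording, with no new patients or data. Power for Radiographic Success stays at or above 90% at a 10% bilateral share; at 20% it could fall to 88.7% if paired knees were perfectly correlated. The downside is that under real heterogeneity the pooled figure is an average, which the separate estimates would show, and a device that does worse in bilateral knees is less likely to pass.

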3.4 ADDITIONAL STUDY POPULATION INFORMATION

3.4.1.PER PROTOCOL (PP) POPULATION

Patients who have complete data (i.e. at radiographic, clinical, and safety) collected per the protocol are the Per Protocol (PP) population. Those cases with complete data for a primary endpoint collected per the protocol at 22+ months or who have had a revision/UADE at or before the 22+ month visit will be used in the analysis of that primary endpoint.

3.4.2. INTENT TO TREAT (ITT) POPULATION

Patients who have met the Inclusion/Exclusion criteria, signed the Informed Consent, and been randomized comprise the ITT population and will be tracked. Those patients that have "fallen out" of the study and did not receive either the investigational or the control device will be summarized by specific reason for not receiving the study device. The primary endpoint will be analyzed for the ITT Population as a sensitivity analysis, with the purpose of evaluating the impact of protocol deviations and missing data on the primary endpoints.

3.4.3. DESIGN ONE PATIENTS

All subjects enrolled in the Design One phase of the IDE will be included in this study group. Where sufficient sample size exists, analysis of all study endpoints will be carried out as described in this plan. However, because the investigational devices in this group have a slightly different design and the patients were randomized under a different plan, the group will be analyzed separately from the Per Protocol and Intent to Treat populations (Design Two Patients).

3.5 ANALYSIS OF STUDY DATA

3.5.1. DESCRIPTIVE STATISITICS INCLUSING PATIENTS' BASELINE STATUS

Subjects in the Cementless and Control groups will be compared regarding a list of baseline items, including Knee Society Assessment and Function Scores, demographics (age, gender), medical history, unilateral vs. bilateral status, and use of pain medication for knee-related and non-knee related issues. Standard statistical tests (chi-square, Cochran-Mantel-Haenszel chi-square, Student's t) will be used.

Equitable numbers of men and women are expected to be enrolled. Therefore, we will not perform a stratified analysis for the primary endpoint or stratify randomization on this variable. However, the proportions of males and females in each group will be summarized and compared as stated above in the analysis of baseline data. In addition, the effect of gender on the primary outcomes at 24 months will be assessed within either a linear regression (for continuous primary endpoints) or logistic regression model (for binary primary endpoints) as described below in the Exploratory Analysis section.

Because this is a randomized study, baseline characteristics are expected to be similar between the two treatment groups. If this is not the case based on statistical tests conducted above, then sensitivity analyses will be conducted to assess the impact of the baseline variable in question on study success. In addition, the effect of the baseline variable in question will be assessed within a linear or logistic regression model as described below in the Exploratory Analysis section.

Baseline characteristics will be examined by center in order to determine if there is any center-to-center heterogeneity. Sites with less than or equal to 5 cases in either treatment arm will be combined to form a "pooled" site for analysis. For categorical baseline variables with polychotomous outcomes, differences between treatment groups will be compared across strata (site) using the Cochran-Mantel Haenszel (CMH) test. For dichotomous baseline characteristics (e.g., male/female, unilateral/bilateral) the Breslow-Day test for homogeneity of odds ratios will be used to test for site*treatment interaction, with the demographic variable treated as the "response". For continuous baseline variables, a separate analysis of variance (ANOVA) will be performed for each continuous variable to assess site-to-site variability. In this model, the demographic variable is treated as the "response" and the treatment group, site, and interaction are model terms. The F-test for the interaction term will be used to assess site dependencies.

If site-to-site variability is found, the distribution of the variable in question will be examined by site graphically and descriptively. In addition, the effect of site and the baseline variable in question will be assessed within a linear/logistic regression model as described in the Exploratory Analysis section. If necessary, sensitivity analyses will be conducted to determine what effect, if any, this variability has on the primary outcome.

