3.0 STATISTICAL ANALYSIS PLAN

This is a two-group, multi-center, randomized clinical trial to compare Biomet's cemented Oxford® Partial Knee System to another active intervention, the Oxford® Cementless Partial Knee System (abbreviations: Control vs. Cementless). Imbalanced, blocked randomization (2:1, Cementless vs. Control) will be implemented.

Randomization will be per patient. In the event that an intraoperative screen failure occurs post-randomization, randomization will not be reassigned and this patient will not count toward the overall sample size. Randomization will continue with the next subject enrolled as previously described. The randomization plan will be produced using SAS v 9.2 for Windows. Randomization will be by center, and each site will receive separate randomization plans using a predetermined block size that will remain undisclosed to the sites. The randomization assignments will be in the form of envelopes to be opened intra-operatively after the first tibial cut and bone quality is assessed against the eligibility criteria.

The primary study endpoint will consist of four (4) individual co-primary endpoints, including both safety and efficacy measures. The following endpoints are included as individual parts of the primary endpoint:

- 1. Knee Society Assessment Score number of points received for the Knee Society Assessment Score at the 22+ month assessment
- 2. Knee Society Function Score number of points received for the Function Score at the 22+ month assessment.
- 3. Revisions or removals of any component of the device or an unanticipated, device-related adverse event (UADE) at any time point. This is a binary endpoint in which a knee is either a "success" or "failure". To obtain a successful result, a knee must reach the 22 + month upper window limit with the device intact and without a component revision/removal or a UADE.
- 4. Radiographic Assessments at the 22+ month assessment

This is a binary endpoint in which a knee is either a "success" or "failure". To obtain a successful radiographic endpoint, a knee must meet the following criteria at the 22+ month

- a. Absence of osteolysis
- b. No migration/subsidence of any femoral or tibial component
- c. Absence of fractured component

Conversely, a radiographic failure is defined as follows:

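### The tests that Section 3.5.1 designates for finding baseline differences between centers do not test for differences between centers

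*Combined protocol and SAP*

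**What the plan says.** SAP Section 3.5.1 states the aim: "Baseline characteristics will be examined by center in order to determine if there is any center-to-center heterogeneity". It then names one test per type of variable.

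- Multi-category: "differences between treatment groups will be compared across strata (site) using the Cochran-Mantel Haenszel (CMH) test".
- Two-category: "the Breslow-Day test for homogeneity of odds ratios will be used to test for site*treatment interaction", with the baseline variable as the response.
- Continuous: "a separate analysis of variance (ANOVA) will be performed for each continuous variable to assess site-to-site variability". In that model "the treatment group, site, and interaction are model terms", and the designated criterion is: "The F-test for the interaction term will be used to assess site dependencies".

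The consequence is conditional: "If site-to-site variability is found, the distribution of the variable in question will be examined by site graphically and descriptively". A regression assessment of site and the variable follows, and sensitivity analyses if needed. No significance level is given for these baseline tests; Section 3.5.6 gives 0.05 for center effects on the outcomes.

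On allocation, Section 3.0 says: "Randomization will be by center, and each site will receive separate randomization plans". The ratio is 2:1 in blocks.

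**The concern.** Whether centers enrolled different patients is a question about the site main effect: does the distribution of age, sex or diagnosis shift from one site to the next? An arm-by-site interaction asks something else, namely whether the gap between the two arms varies by site. CMH asks a third question, whether the arms differ on average after adjusting for site. One stated aim is thus served by two different questions, neither of which matches it.

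The mismatch matters because allocation is randomized separately at each center. A characteristic fixed before allocation then has no true arm difference at any site and no true arm-by-site interaction. A test of either should reject only at its nominal level, even if one site enrolls patients far older than another. The by-site plots and further analyses hang on these tests, so the trigger would carry almost no information about what it is meant to detect.

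**Working it through.** **Inputs from the documents.** 383 in total, 255 and 128 (Section 3.3); at most 12 sites (Section 2.4); 2:1 blocked allocation within center (Section 3.0).

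**Assumed, because the documents give no figure.** Level 0.05 for the baseline tests; block size 6; equal sites, 6 or 12 of them; independent knees; and the size of the true site differences, shown as a range. With 12 equal sites, 383/12 = 31.9 per site, or about 21 and 11 by arm, so the rule that pools sites with five or fewer cases in an arm would not apply.

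**The plan's own figure.** The SAP gives no figure for the baseline tests, so only the total N was reproduced. With success 0.95 in both arms, margin 0.08, one-sided 0.05 and power 0.90:

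n(control) = (1.645 + 1.282)² × [0.95 × 0.05 + (0.95 × 0.05)/2] / 0.08² = 8.564 × 0.07125 / 0.0064 = 95.3, hence 96; cementless 2 × 95.3 = 190.7, hence 191.

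Dividing by 0.75 for the 10% and 15% allowances gives 191/0.75 = 254.7 and 96/0.75 = 128, hence 255 and 128, total 383. The plan's N is reproduced.

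**Why the planned tests cannot see site differences.** Write a continuous baseline value as y = μ + s(j) + e, where s(j) is the shift of site j and e is independent of arm because allocation is random within site. The arm difference at site j is mean(e, cementless) − mean(e, control). The shift s(j) cancels, so the interaction F-test does not depend on it. For a two-category variable with prevalence p(j) in both arms, the odds ratio at site j is 1 whatever p(j) is, so Breslow-Day has nothing to find. CMH compares the arms within each site's own margins, so differences between sites drop out there too.

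**Simulation.** Rejection rates at 0.05, planned test against a direct site test (site F-test, or site-by-category chi-square). Site differences are the intraclass correlation (ICC, between-site share of variance) for ANOVA, and the between-site SD on the logit or log-weight scale for the other two.

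| Planned test | Site difference | 6 sites: planned / direct | 12 sites: planned / direct |
|---|---|---|---|
| ANOVA interaction F | ICC 0 | 5.0% / 5.3% | 4.8% / 4.8% |
| | ICC 0.02 | 4.8% / 43% | 5.3% / 36% |
| | ICC 0.05 | 4.8% / 76% | 4.7% / 76% |
| | ICC 0.10 | 5.1% / 92% | 4.8% / 96% |
| | ICC 0.20 | 5.4% / 98.7% | 4.5% / 99.9% |
| Breslow-Day | SD 0 | 5.3% / 4.9% | 5.2% / 5.1% |
| | SD 0.5 | 5.4% / 81% | 5.2% / 80% |
| | SD 1.0 | 4.8% / 98% | 5.3% / 99.7% |
| CMH, 3 levels | SD 0 | 6.3% / 4.2% | 5.2% / 6.1% |
| | SD 0.5 | 4.8% / 98% | 4.2% / 99% |
| | SD 1.0 | 5.7% / 100% | 4.6% / 100% |

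There were 3,000, 1,000 and 1,500 replicates per cell for the three tests. The Monte Carlo standard error of a 5% rate is √(0.05 × 0.95/3000) = 0.4 points for ANOVA, and 0.7 and 0.6 points for the other two. The planned tests lie between 4.2% and 6.3% throughout, with no trend as the site differences grow.

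**The case against.** The strongest defense is that the tests are sensible under another name. Allocation uses envelopes held at the sites and opened during surgery, so checking that arm balance is consistent across sites has a purpose. That stands, and it is a reason not to drop the tests. It does not rescue them for the stated aim, and CMH would not serve the alternative aim fully either, because it tests the average arm difference and not whether that difference varies by site.

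Some stronger readings are tempting, but the documents do not support them.

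- A reader might infer that every significant result would be a chance finding. That is too absolute. A contralateral study knee receives the matching device without randomization (note to Section 2.2), and unilateral or bilateral status is one of the variables named for testing. Intraoperative screen failures after randomization do not count toward the sample (Section 3.0), and the primary analysis follows the implanted device (Section 3.5.2). Real arm-by-site imbalance can arise by these routes.
- A reader might infer that site differences are ignored altogether. They are not: the ANOVA already contains a site term, and the regression models in Section 3.5.6 include site and the main baseline covariates whatever these tests show.
- A reader might infer that pooling, or the trial's conclusion, rests on these tests. Section 3.5.6 ties pooling across centers to the treatment-by-center test on outcomes, and Appendix B ties it to eligibility and adherence. None of the four primary tests uses the baseline checks. With randomization by center, a site difference in a baseline variable does not by itself bias the arm comparison.
- A reader might count the tests: with 8 or 10 independent variables, 1 − 0.95⁸ = 34% or 1 − 0.95¹⁰ = 40% for at least one false alarm. Any replacement at the same level would have the same rate when sites do not differ, so this is no argument against these tests in particular.

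It is also fair that site main-effect tests would flag many variables, 76% of the time at an ICC of 0.05. That is a cost of answering the stated question.

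**Conclusion.** The point holds in a limited form. Section 3.5.1 asks whether baseline characteristics differ between centers and designates three tests that do not address it. For knees randomized as planned they reject at about the nominal level however large the site differences are, while a direct site test with 12 sites has from 36% power (ICC 0.02) to 99.9% (ICC 0.20) for continuous variables. The follow-up conditional on these tests is therefore set off mostly by chance and rarely by real site differences.

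The power figures depend on the assumed site differences, level, block size and equal sites. The failure of the planned tests to respond does not depend on how large the site differences are; it follows from allocation within center. The damage is confined to the descriptive and exploratory assessment of sites.

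**What to change.** In Section 3.5.1:

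1. For the stated aim, use the site main effect: the site F-test from the ANOVA for continuous variables, and a site-by-category chi-square (exact if sparse) for two-category and multi-category variables. State the significance level.
2. Present baseline summaries by site regardless of any p-value.
3. Keep the interaction F-test, Breslow-Day and CMH only if relabelled as checks of arm balance across sites, separate from the question of differences between centers.

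Leave the outcome interaction test in Section 3.5.6 as it is.

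The cost is SAP wording; no new data are needed, and the site term is already in the ANOVA. The downside is that formal site tests will send more variables to descriptive follow-up.
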